4.6.3. Laboratory Data

Clinical laboratory values will be expressed using the International System of Units (SI), except g/dL and 10⁹/L will be used for hemoglobin and nucleated erythrocytes, respectively. Values will be summarized for each clinical laboratory parameter, including hematology, clinical chemistries, and iron studies, as specified below, and in the schedule of events.

The laboratories' own reference ranges are used as the default. In the absence of these ranges, refer to the Global Reference Range (GRR) Sources identified in [Table 6](#). Age- and sex-specific ranges will be used to flag out of range values and to indicate CTCAE (version 4.03) grade, where applicable.

The versions of the GRRs being utilized for this study are footnoted below. If revised GRRs are published during the study, the version will not automatically update.

Table 6. Global Reference Range Sources

Source	Version	Purpose
Kratz A, et al. "Laboratory Reference Values". N Engl J Med. 2004;351: 1548-63.	N Engl J Med. 2004;351: 1548-63	Adult Ranges
Mayo Clinic	Updated regularly online ^[1]	Children Ranges
Brown A. NHS Blood Sciences Department of Immunology and Immunogenetics. "Immunology Age Related Reference Ranges". QPR No. IMMQ0066.	Version No. 1.4	Immunology Age-Related Reference Ranges
Shearer W, et al. "Lymphocyte subsets in health children from birth through 18 years of age: The Pediatric AIDS Clinical Trials Group P1009 study." J Allergy Clin Immunol. 2003; 112: 973-80.	J Allergy Clin Immunol. 2003; 112: 973-80.	Lymphocyte Subsets in Pediatrics ages 0 to 18

^[1]<https://www.mayocliniclabs.com/test-info/pediatric/refvalues/index.html>

Descriptive statistics on the laboratory parameters listed in [Table 7](#) below, but may not be limited to, will be presented by visit, and where applicable, change from baseline will also be provided.

Table 7. List of Laboratory Parameters

Hematology	Iron Contents

 • Complete blood count (CBC) with differential • Haptoglobin • Nucleated erythrocytes • Platelet count • Reticulocyte count • Methemoglobin • Red cell distribution width (RDW) 	
 • Iron saturation (transferrin saturation) • Serum ferritin • Serum transferrin receptor • Serum transferrin • Liver iron content • Cardiac iron content (if assessed at baseline)
Serum Chemistry and Liver Function	

 • Albumin • Bicarbonate • Blood urea nitrogen • Calcium • Chloride • Creatinine • C-reactive protein (CRP) • eGFR • Erythropoietin • Glucose • Magnesium 	
 • ALP (Alkaline phosphatase) • ALT (Alanine aminotransferase) • AST (Aspartate aminotransferase) • GGT (Gamma-glutamyl transferase) • LDH (Lactate dehydrogenase) • Total, direct and indirect bilirubin • Phosphate • Potassium • Sodium • Total protein • Uric acid
Immunology	

 • CD3 • CD4 • CD8 • CD19 • CD16/CD56 	
 • Estradiol (females only) • Total testosterone (males only) • TSH, Free T3, Free T4 • Cortisol • ACTH • FSH • LH
Coagulation	
	
 • Prothrombin time (PT) • Activated partial thromboplastin time (aPTT) • D-Dimer

Urinalysis including protein, microalbumin, glucose, ketones, pH, specific gravity, and occult blood will be listed. Additional clinical laboratory tests may be performed at the Investigator's discretion and will be listed.

Shift tables from baseline which indicate abnormally high or abnormally low laboratory parameter value grades based on CTCAE criteria will be performed using the highest or lowest abnormal value in the following time period intervals: "MB to < C", "C to < NE", "NE to M12", ">M12 to M24", "D1 to < NE", and "D1 to M24" (see definitions of the time period intervals in Section 3.11).

The parameters included in the CTCAE shift tables and the direction for CTCAE can be found in [Table 8](#).

Table 8. Selected Laboratory Tests – Direction (Increase or Decrease) for CTCAE

Category	Laboratory test	Direction for CTCAE
Hematology	Absolute neutrophils count	Decrease
	Hemoglobin	Both
	Leukocytes	Decrease
	Lymphocyte	Both
	Platelets	Decrease
Chemistry	Albumin	Decrease
	ALP	Increase
	ALT	Increase
	AST	Increase
	Calcium	Both
	Creatinine (serum creatinine)	Increase
	eGFR	Decrease
	GGT	Increase
	Glucose	Both
	Magnesium	Both
	Phosphate	Decrease
	Potassium	Both
	Sodium	Both
	Total Bilirubin	Increase
Coagulation	Activated thromboplastin time	Increase

Hematology and chemistry parameters will be also assessed for potentially clinically significant (PCS) abnormal criteria. Lab results that meet the PCS criteria will be listed and summarized based on lab time periods indicated in [Section 3.11](#). The PCS thresholds used are listed in [Table 9](#).

Summary of \geq Grade 3 cytopenia (i.e., decreased platelets, neutrophils or hemoglobin) will be presented for the TP subjects at risks on or after Day 60, and on or after Day 100.

Laboratory values for selected hematology and chemistry parameters may be presented graphically as appropriate. If data allow, boxplots may be provided as well.

All laboratory data will be provided in data listings. A subset listing will be presented for all subjects with any laboratory values \geq Grade 3 based on CTCAE version 4.03 criteria.

Table 9. Potential Clinically Significant Abnormal Criteria for Hematology and Chemistry Parameters

Category	Test Name	Potentially CS – Low if observed value is:	Potentially CS – High if observed value is:
Hematology			
	ANC	$<1.5 \times 10^9/L$	$>13.5 \times 10^9/L$
	Basophils		$>1.6 \times 10^9/L$
	Eosinophils		$>1.6 \times 10^9/L$
	Erythrocytes	$\leq 3.5 \times 10^{12}/L$	$\geq 6.4 \times 10^{12}/L$
	Hemoglobin	$< 8 \text{ g/dL}$	$>16 \text{ g/dL}$
	Leukocytes	$<3.0 \times 10^9/L$	$\geq 16 \times 10^9/L$
	Lymphocytes	$<0.8 \times 10^9/L$	$>12 \times 10^9/L$
	Monocytes		$>2.5 \times 10^9/L$
	Platelets	$\leq 75 \times 10^9/L$	$\geq 700 \times 10^9/L$
Chemistry			
Liver	ALT		$\geq 3 \times \text{ULN}$
	AST		$\geq 3 \times \text{ULN}$
	ALP		$\geq 3 \times \text{ULN}$
	Total bilirubin		$\geq 34.2 \text{ umol/L}$
	Direct bilirubin		$\geq 7.0 \text{ umol/L}$
Renal	Creatinine (serum creatinine)		$\geq 176.8 \text{ umol/L}$
	Urea Nitrogen		$\geq 10.7 \text{ mmol/L}$
Electrolytes	Sodium	$\leq 126 \text{ mmol/L}$	$\geq 156 \text{ mmol/L}$
	Potassium	$\leq 3 \text{ mmol/L}$	$\geq 6 \text{ mmol/L}$
	Chloride	$\leq 90 \text{ mmol/L}$	$\geq 118 \text{ mmol/L}$
Other	Glucose	$\leq 2.22 \text{ mmol/L}$	$\geq 9.71 \text{ mmol/L}$

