2.2.3. Safety Endpoints

Safety will be evaluated by the following:

- Safety and tolerability of plerixafor for mobilization
- Success and kinetics of HSC engraftment
- Transplant-related mortality through 100 days post-drug product infusion and through 365 days post-drug product infusion
- Detection of vector-derived replication competent lentivirus (RCL) in any subject
- The number of subjects with insertional oncogenesis (myelodysplasia, leukemia, lymphoma, etc.)
- The number of subjects with persistent oligoclonality
- Frequency and severity of AEs/SAEs
- Laboratory parameters over time, including the following immunology tests:
Screening for irregular antibodies, lymphocyte subpopulation evaluation (CD3, CD4, CD8, CD19, CD16/CD56)
- Incidence of acute and/or chronic graft-versus-host disease (GVHD)
- Other safety labs over time: chemistries, LFTs (AST, ALT, ALP, GGT, bilirubin [total and direct]), hematology, coagulation parameters
- Hormonal testing over time: estradiol (females only); total testosterone (males only) TSH, free T3, free T4, cortisol, ACTH, FSH, LH (all subjects)
- Change from baseline in methemoglobin concentration at Month 12 and Month 24
- Number of subjects with presence of a chromosomal abnormality or genetic mutation associated with hematologic malignancies over time

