3.5. Methods of Pooling Data

Data will be presented by group. Efficacy analyses will focus on Group C. However, an overall column will be included as appropriate.

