3.8. Subgroups

To assess the consistency in treatment effects across difference subgroup levels, subgroup analyses may be explored for efficacy endpoints, such as VOE-CR and sVOE-CR. Subgroup analyses will include, but may not be limited to, age group (adolescents [≥ 12 and < 18 years old at Informed Consent] versus adults [≥ 18 years old at Informed Consent]), sex, race, alpha-globin genotype, and/or stroke history (Yes/No).

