4.6.1. Adverse Events

AE collection windows for Groups A and B are different than those for Group C, and the details can be found in [Section 1.2.1](#). All AEs will be coded via MedDRA coding system (version 23.0 or higher) and displayed in tables and listings using SOC and PT. The safety analyses will include evaluation of all AEs and of treatment-emergent AEs. The terminology "treatment-emergent" is reserved for events that occur during or after drug product infusion.

Summaries of AEs related to drug product will be based on the investigator's assessment; an assessment of 'Possibly Related', 'Related' or missing (if AE occurred after drug product

infusion) will be considered related to drug product. AEs will be summarized by the time intervals mentioned in [Section 3.11](#). For treatment-emergent AEs, only the following time intervals will be presented: "D1 to <NE" which is from drug product infusion to the latest date prior to initiation of neutrophil engraftment, "NE to M24", and "D1 to M24". The number of subjects "at risk" in each time interval will also be provided in summary tables. Subjects who are lost to follow-up, withdrew from the study, or died prior to the beginning of the time interval will be excluded from the number "at risk" in the time interval.

Summary information (the number and percentage of subjects by SOC and PT, separated by group and by time interval) will be tabulated for:

- All AEs
- Treatment-emergent AEs
- Serious AEs (SAEs)
- Treatment-emergent SAEs
- Grade 3 or higher AEs
- Grade 3 or higher treatment-emergent AEs
- Treatment-emergent AEs related to drug product
- Treatment-emergent SAEs related to drug product
- AEs attributed to SCD
- AEs attributed to SCD post Month 6
- SAEs attributed to SCD
- SAEs attributed to SCD post Month 6
- AEs attributed to cell procurement (bone marrow harvest ^[1] and mobilization/apheresis ^[1])
- Grade 3 or higher AEs onset within 7 days post plerixafor
- AEs attributed to conditioning ^[1]
- AEs attributed to study procedure ^[1]
- AEs from Informed Consent to Month 24 visit by selected subgroups (as specified in [Section 3.8](#) as appropriate), to be presented in two time intervals: "ICF to M24" and "D1 to M24".
- AEs by maximum severity (overall and by selected subgroups)
- Events of interest (search criteria in [Appendix 6.7](#))

^[1] Based on attribution on CRF for events as reported by investigators

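### The planned FSH and LH summaries do not separate men from women, and no planned laboratory table counts out-of-range hormone values

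*SAP*

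**What the plan says.** Protocol 2.2.3 lists the endpoint as "Hormonal testing over time: estradiol (females only); total testosterone (males only) TSH, free T3, free T4, cortisol, ACTH, FSH, LH (all subjects", and SAP 1.2.6.6 repeats it. Protocol Tables 2 and 4 schedule hormone samples at Screening, Month 12 and Month 24.

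SAP 4.6.3 plans descriptive statistics for the Table 7 parameters that "will be presented by visit, and where applicable, change from baseline will also be provided". In Table 7 the rows beginning "Estradiol (females only" and "Total testosterone (males only" are each confined to one sex. FSH and LH carry no restriction.

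The presentation rule in SAP 3.5 is "Data will be presented by group", with an overall column where suitable. SAP 3.8 names sex and age group as subgroup factors, but for efficacy: "subgroup analyses may be explored for efficacy endpoints, such as VOE-CR and sVOE-CR". SAP 4.6.1 carries these subgroups over to adverse events, in the item "AEs from Informed Consent to Month 24 visit by selected subgroups". Section 4.6.3 has no counterpart for laboratory data.

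Table 8 covers hematology, chemistry and coagulation; Table 9 covers hematology and chemistry. Neither contains a hormone. The same section says that out-of-range values are flagged against ranges specific to age and sex, where these apply, and that all laboratory data are listed.

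**The concern.** A programmer who follows these rules produces one FSH row and one LH row per visit within each study group. The trial takes men and women aged 12 to 50, all of whom are to receive myeloablative busulfan. Protocol 6.2.10 provides for sperm, testicular tissue or oocyte banking before conditioning. Gonadal function is therefore a foreseeable safety question, and these two hormones are part of the endpoint that addresses it.

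If levels or changes differ between the sexes, the pooled mean and median describe neither sex and depend on how many of each are in the group. The SAP already accepts that normal values can differ by sex and age, because it flags against sex- and age-specific ranges. For hormones, no laboratory table counts those flags. A reader of the summary tables could not say how many women or men moved from normal to high FSH or LH.

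**Working it through.** **Step 1: where each hormone result would appear.**

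| Planned output | Hormones included | Split by sex |
|---|---|---|
| Table 7, by visit: estradiol | yes | females only |
| Table 7, by visit: testosterone | yes | males only |
| Table 7, by visit: FSH, LH | yes | none stated |
| Table 8, CTCAE shift | none | not relevant |
| Table 9, potentially clinically significant values | none | not relevant |
| AE tables, SAP 4.6.1 | only if the abnormality is reported as an AE | possible, not fixed |
| Laboratory listings | all | by subject |

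No summary table gives FSH or LH by sex, and no laboratory table counts out-of-range values for any hormone.

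**Step 2: what pooling could do. This is an illustration on assumptions only.** The plan states no figure to reproduce. It gives no number of subjects by sex and no hormone levels. The one documented input is the 36 subjects infused in Group C (SAP Table 1).

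Assume that one sex changes by d = 5 within-sex SD and the other by 0. With n of N = 36 in the affected sex, the pooled mean change is (n/N) × d. The pooled variance is about 1 + (n/N)(1 − n/N) × d² × N/(N − 1). Medians and maxima come from simulation (4,000 replicates).

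| n affected of 36 | Pooled mean | Pooled median | Pooled SD | Maximum |
|---|---|---|---|---|
| 11 | 11/36 × 5 = 1.53 | 0.57 | 2.54 | 6.57 |
| 18 | 18/36 × 5 = 2.50 | 2.50 | 2.72 | 6.81 |
| 25 | 25/36 × 5 = 3.47 | 4.42 | 2.53 | 6.97 |

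SD check for n = 11: 1 + 0.306 × 0.694 × 25 × 36/35 ≈ 6.46, and its square root is 2.54.

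A table by sex would show about 5 in one sex and 0 in the other in every row. The pooled mean is 31% (11/36) to 69% (25/36) of the true change.

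A second illustration assumes a post-infusion FSH median of 10 IU/L in men and 60 in women, all women affected, and a log-SD of 0.4. With 11, 14, 18 or 21 women of 36, the pooled median is about 13, 14, 25 or 40 IU/L, while the women's own median stays near 60. The pooled SD is 29 to 34, against about 4 if the women were unaffected (assumed median 6).

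Both cases are extreme: everyone in one sex is affected and no one in the other. They show that pooling dilutes the change and loses its link to sex. The raised SD and the maximum show that it does not erase the signal.

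**The case against.** A reader might infer that gonadal failure in one sex cannot be read from the hormone endpoint at all. The documents do not support that, for four reasons.

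- Estradiol and testosterone belong to the same endpoint and are each summarized within one sex.
- All laboratory values are listed, with age- and sex-specific flags where these apply. For the 36 infused in Group C, two scheduled post-infusion visits give about 36 × 2 = 72 values per hormone, which can be read by hand.
- Protocol 6.2.30.4 makes any clinically significant laboratory abnormality an AE. Group C records all AEs through the Month 24 visit (Protocol 6.2.30.1), and SAP 4.6.1 allows AE tables by the Section 3.8 subgroups, which include sex. In Groups A and B, lower-grade AE collection stops earlier.
- SAP 3.2 asks for SD, minimum and maximum as well as mean and median, so a pooled table would still hint at a problem.

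It is also fair to say that pooling is inferred from silence: no sentence says that the sexes will be combined. The SAP leaves room for further parameters and for shift tables, and Protocol 7.4.5 permits further safety summaries. The lack of hormones in Tables 8 and 9 applies to every hormone, not just these two.

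These points dispose of the stronger reading. They do not close the gap. Permission to add a table is not a commitment to produce it, listings leave the reader to count cases, and the AE route depends on the investigator's judgment of clinical significance.

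**Conclusion.** The point holds in limited form. As written, the FSH and LH summaries mix men and women, and no planned laboratory table counts out-of-range hormone values, although the ranges needed are already specified. That part of a named safety endpoint is hard to interpret. It would be wrong to conclude that gonadal toxicity would go unseen.

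The conclusion rests on the usual reading of the SAP: where no sex split is stated, none is made. Its practical size is unknown, because the documents give neither sex counts nor hormone levels and the numerical illustrations rest on assumed values. No primary or key secondary analysis depends on it. It is a minor improvement, worth making because it costs little.

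**What to change.** In SAP 4.6.3:

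1. Present FSH and LH, observed values and change from baseline, separately for females and males.
2. Add counts of low/normal/high shifts by sex, from baseline to Month 12 and to Month 24, for FSH, LH, estradiol and testosterone (the last two in their own sex). Use the age- and sex-specific ranges already specified and the Month 12 and Month 24 windows in SAP Table 12.
3. List subjects under 18 separately if cells are small.

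The cost is a few extra tables from samples already scheduled. The drawback is small cells, mainly for adolescents and for Groups A and B.

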4.6.4. Vital Signs, Physical Examination and Performance Status

Vital signs include systolic/diastolic blood pressure, heart rate, respiration rate, and temperature, and will be performed in accordance with institutional standards and as per the SOE.

A summary table of the number and percentage of subjects with PCS abnormal criteria for vital signs and physical examination parameters at any point during the study will be presented for

pre- and post-infusion time periods. The criteria for determining PCS abnormal criteria values in vital signs can be found in [Table 10](#).

Table 10. Potential Clinically Significant Abnormal Criteria for Vital Signs and Physical Examinations

Variable Name	PCS – Low if:			PCS – High if:		
	Observed Value is:	AND	Decrease from Baseline is:	Observed Value is:	AND	Increase from Baseline is:
SBP	<90 mmHg		≥20 mmHg	>160 mmHg		≥20 mmHg
DBP	<50 mmHg		≥10 mmHg	>95 mmHg		≥10 mmHg
Heart Rate	<50 bpm		≥15 bpm	>120 bpm		≥15 bpm
Weight	≥ 10% decrease from baseline			≥ 10% increase from baseline		
Height				≥ 2 inches increase from baseline		

DBP = diastolic blood pressure; SBP = systolic blood pressure

Performance status, Karnofsky score, or Lansky score will be assessed at multiple time points prior to drug product infusion and at all scheduled follow-up visits. A listing will be provided. Tanner staging will only be presented in data listings.

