Subjects in Group B2 who tolerated and effectively mobilized with plerixafor were given the option to postpone drug product manufacture until Group C opened, to allow drug product manufacture using plerixafor mobilized cells. In Group C, subjects for whom adequate HSCs are collected to achieve the minimum cell dose but not for rescue, and who do not tolerate plerixafor or do not effectively mobilize with plerixafor may be offered the option of bone marrow harvest for collection of back-up cells only, provided that drug product manufactured from mobilized cells has met criteria for dispositioning for clinical use.

As of Version 8.0 of this protocol, Group C will include adolescent subjects ≥ 12 and < 18 years of age in addition to subjects ≥ 18 and ≤ 50 years of age. It should also be noted that while all Group A subjects and some Group B subjects received drug product manufactured using “Process 1”, all current and future Group C subjects will receive drug product manufactured using an optimized process termed “Process 2”. Treatment with drug product manufactured using Process 2 (versus Process 1) has resulted in increased drug product VCN, peripheral blood VCN, and HbA^{T87Q} levels across multiple bluebird bio-sponsored clinical studies.

The drug product must be release tested and dispositioned for clinical use and stored at the study site before the subject can begin myeloablative conditioning with busulfan.

Stage 3 –Myeloablative conditioning and infusion of bb1111

The subject’s suitability for transplant will be reconfirmed with clinical laboratory tests (complete blood count [CBC], serum chemistry, liver function tests, and pregnancy test), physical examination, performance status, cytogenetics, and other tests based on institutional requirements. The results of these tests will be reviewed, and availability of the drug product on site and the availability of back-up cells will be confirmed before the site can proceed with conditioning.

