5.5. Duration of Subject Participation

Time between Screening and drug product infusion will be variable and is estimated generally to be between 3 to 5 months (e.g., up to 3 months between Screening and Mobilization, followed by approximately 2 months before drug product infusion). Thereafter the subject is planned to remain on study for approximately 24 months. Eligible subjects are then expected to enroll in a separate long-term follow-up study until approximately 15 years post-drug product infusion. For subjects enrolled in Group B2 who opted to defer manufacture of drug product until Group C opened, the time between Screening and drug product infusion was extended as long as the subject continued to meet eligibility criteria.

If the subject is unable to undergo mobilization for drug product manufacture within approximately 3 months of the initiation of Screening, some assessments may need to be repeated to confirm continuing eligibility or to provide a reliable baseline prior to study procedures. In particular, physical exam, vital signs, performance status, HRQoL, echocardiogram, complete blood count, chemistry, urinalysis, and liver function tests, and for women of child-bearing potential, tests for pregnancy, must be performed within 3 months of proceeding to evaluation for mobilization. For subjects with exposure risks for HIV, HBV and HCV, these tests should also be repeated. Some of these assessments may be performed immediately prior to mobilization, as specified in the SOE. Where clinically and/or regionally indicated, other tests for infectious pathogens may be performed, as required by regional regulations or at physician discretion. Other blood tests, including those for immune subsets, hormonal or dyserythropoiesis testing only need to be repeated if more than 6 months have transpired, unless there is clinical concern due to an initial screening test (e.g., borderline thyroid function). Cerebral MRA/MRI and echocardiogram performed within 3 months of ICF and PFT results performed within 6 months of ICF may be used, unless there is clinical indication for repeat testing, or initial testing was borderline. The need for liver biopsy should be guided by MRI findings, as described in the protocol, unless a biopsy performed within 1 year of mobilization exhibited no evidence of fibrosis or hepatitis. Sickle cell disease genotyping, baseline VCN, baseline RCL and baseline β^{A-T87Q} -globin, once performed, do not have to be repeated.

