Work Productivity Assessment (WPAI)/Caregiver WPAI-GH ²⁶			X		X		X		X		X
Cognitive Function Assessments: PROMIS Short Form 6a ²⁶			X		X		X		X		X
Vaso-occlusive event collection	Continuous from ICF signing ²⁷										
Adverse event collection	Continuous from ICF signing										
Concomitant medication collection	Continuous from ICF signing										

¹ Any leg (skin) ulceration noted upon physical exam or as part of medical history must include severity classification.

² Chronic pain will be assessed using the AAPT Diagnostic Criteria for Chronic Pain Associated with SCD (see [Section 6.2.6](#)).

³ Karnofsky performance status (≥ 16 years of age) or a Lansky performance status (< 16 years of age).

⁴ Vital signs include systolic/diastolic blood pressure, pulse, temperature, oxygen saturation, weight, and height.

⁵ CBC with differential should be carried out whenever ISA is performed.

⁶ Hematology will include CBC with differential, nucleated erythrocytes, platelets and reticulocytes. Subjects should get platelet count monitored approximately weekly and at least 8 days after the most recent platelet transfusion until platelet engraftment.

⁷ Chemistry will include sodium, potassium, chloride, bicarbonate, blood urea nitrogen, creatinine, calcium, magnesium, phosphate, albumin, total protein, uric acid, LDH, liver enzymes (GGT, ALP, ALT, AST, direct and total bilirubin), glucose and CRP at every visit.

⁸ Coagulation analysis includes PT/aPTT, D-Dimers.

⁹ Iron studies include the following: serum iron, serum ferritin, serum transferrin, iron saturation (transferrin saturation), and serum transferrin receptor. Iron studies should be performed prior to restarting iron chelation, if needed.

¹⁰Hormonal testing will include: Estradiol, (females only); total Testosterone (males only); TSH, free T3, free T4, AM cortisol, ACTH, 25 OH Vitamin D, PTH, FSH, LH (all subjects).

¹¹Urinalysis includes color, appearance, specific gravity, pH, microalbumin, protein, creatinine, glucose, ketones, occult blood.

¹²T cells (CD3), T cell subsets (CD4, CD8), B cells (CD19), natural killer cells (CD16/CD56), and antibody titers against tetanus, pneumococcus, and measles/mumps/rubella.

¹³For subjects who receive final pRBC transfusion after the Month 3 Visit, screening for new irregular antibodies must be performed at the scheduled visit occurring immediately after last pRBC transfusion.

¹⁴VCN is to be carried out whenever ISA is performed.

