3.4. Baseline Definitions

For annualized number of endpoints, such as annualized number of VOEs, sVOEs, hospitalizations and pRBC transfusions, baseline will be defined as the annualized number of the corresponding endpoint in the 24 months before Informed Consent.

The definition of baseline total Hb for Globin Response derivation can be found in [Section 1.2.6.2](#). The baseline total Hb values are collected on the eCRF page of Baseline Hemoglobin. A subject will be considered as having no baseline Hb for Globin Response analysis if the subject has 1 or 0 qualifying Hb value from the Baseline Hemoglobin eCRF page.

For liver biopsy, liver MRI, Cardiac MRI, cerebral MRA/MRI, echocardiogram (including LVEF and TRJV), bone mineral density (BMD) and pulmonary function test (PFT), baseline will be defined as the first assessment during screening. If no records at screening, the last assessment prior to Informed Consent will be used.

Unless otherwise specified, for other efficacy, pharmacodynamic, and safety parameters, including shifts in key laboratory parameters, baseline will be defined as the first assessment during screening (which can be identified by the first record on or after date of Informed Consent Form [ICF], but before initiation of stem cell collection).

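### The height criterion in SAP Table 10 looks only for a gain and ignores age and sex, so it flags growing adolescents as potentially abnormal and can never flag absent growth

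*SAP*

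**What the plan says.** SAP Section 4.6.4 plans "A summary table of the number and percentage of subjects with PCS abnormal criteria for vital signs and physical examination parameters at any point" in the study, shown separately before and after infusion. The thresholds stand in Table 10, titled "Potential Clinically Significant Abnormal Criteria for Vital Signs and Physical Examinations". Blood pressure, heart rate and weight each have a low and a high criterion; for weight the low one is a fall of at least "10% decrease from baseline", and the high one is a rise of the same size. Height has only a high criterion, at least "2 inches increase from baseline", and its low cells are empty. Neither the weight row nor the height row depends on age or sex.

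Three other provisions matter:

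- Protocol Section 3.1 states that from Version 8.0 "Group C will include adolescent subjects", aged 12 to under 18, alongside adults up to 50.
- A footnote to the follow-up schedule (Protocol Section 6.1, Table 4) reads "Vital signs include systolic/diastolic blood pressure, pulse, temperature, oxygen saturation, weight, and height", and vital signs are taken at every visit from Month 1 to Month 24.
- Under the general rule in SAP Section 3.4, "baseline will be defined as the first assessment during screening (which can be identified by the first record on or after date of Informed Consent" and before stem cell collection. Change in height is therefore counted from screening, not from infusion.

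**The concern.** An increase in height is what one expects of a subject who is still growing, yet it is the only height change that Table 10 treats as potentially abnormal. An adult who has finished growing cannot gain 2 inches. Apart from errors in the data, the height row will therefore pick out adolescents because they are growing. The change that a safety reader would want to see in a 12- to 17-year-old, little or no growth, has no criterion. The height row would then answer the wrong question for the only subjects in whom height is expected to change. The rule for a 10% weight gain has the same weakness, because a growing adolescent can meet it without any clinical event.

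**Working it through.** The plan states no figure to reproduce here. The check is how fast a subject must grow to be flagged, and what happens below that rate.

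**Inputs from the documents**

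- Threshold: 2 inches = 2 × 2.54 = 5.08 cm (SAP Table 10).
- Screening to infusion: Protocol Section 5.5 says this "is estimated generally to be between 3 to 5 months".
- Follow-up after infusion: about 24 months (same section).
- Baseline to last height: 24 + 3 = 27 months to 24 + 5 = 29 months.

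**Input not in the documents**

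- Adolescent growth velocity. A range of 0 to 8 cm/year is assumed, taken as constant over time.

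**Velocity that trips the flag by Month 24** = 5.08 / (months / 12)

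- 27 months: 5.08 / 2.25 = 2.26 cm/year.
- 29 months: 5.08 / 2.417 = 2.10 cm/year.
- For comparison, counting from infusion only (24 months): 5.08 / 2 = 2.54 cm/year.

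**Behaviour across the assumed range.** Months from baseline to the flag = 5.08 / velocity × 12; gain in inches = velocity × (27 or 29) / 12 / 2.54.

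| Velocity (cm/year) | Months to flag | Gain at 27 to 29 months (inches) | Flagged by Month 24? |
|---|---|---|---|
| 0 | never | 0 | No |
| 1 | 61.0 | 0.89 to 0.95 | No |
| 2 | 30.5 | 1.77 to 1.90 | No |
| 2.5 | 24.4 | 2.21 to 2.38 | Yes |
| 4 | 15.2 | 3.54 to 3.81 | Yes |
| 6 | 10.2 | 5.31 to 5.71 | Yes |
| 8 | 7.6 | 7.09 to 7.61 | Yes |

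The flag separates subjects growing at about 2.1 to 2.3 cm/year or faster from everyone else. Growth at 2.5 cm/year and at 8 cm/year gives the same result by Month 24. A subject with no growth is not flagged, however long the follow-up.

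**Weight.** A 10% gain over 27 to 29 months is an average of 10 / 2.25 = 4.4% to 10 / 2.417 = 4.1% of baseline weight per year. The documents give no adolescent weight velocities, so how often growth alone would reach this is not estimated.

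**Other programmed rules.** None in the SAP covers growth. Tanner staging is listed only (Section 4.6.4). Hormones are summarised by visit without a growth criterion (Section 4.6.3). The events of interest in Appendix 6.7 do not include growth.

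**The case against.** The strongest reply is that little depends on this table. It is descriptive, in a single-arm study, and no hypothesis test, success criterion or stopping rule uses it. The label says potential significance, which invites review and is not a finding. Growth problems also have other routes to the reader. Physical examination and height are done at each follow-up visit, and Tanner staging every 6 months during puberty (Protocol Section 6.2.3). A clinically significant finding must be recorded as an adverse event (Protocol Section 6.2.30.4). Adverse events are tabulated by selected subgroups, with adolescents against adults among those named (SAP Sections 3.8 and 4.6.1), and by-subject listings are planned (SAP Section 3.2). All of this stands. It limits the point to one table but does not make the height row informative.

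A reader might also infer more than the documents support:

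- *That the table misses growth failure caused by busulfan.* The effects that Protocol Section 6.2.30.2 gives for busulfan do not include impaired growth, and growth is not a safety endpoint. The gap exists whatever the cause.
- *That a flag marks healthy growth.* About 2.1 to 2.3 cm/year is enough to trip it, so a flag shows neither health nor harm.
- *That the PCS counts as a whole are inflated.* Section 4.6.4 specifies no pooled count of subjects with any PCS value. If the output follows Table 10 variable by variable, the blood pressure and heart rate counts are unaffected.
- *That slowed growth is invisible.* The routes above remain open; they depend on the investigator's judgment or on someone reading a listing.

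**Conclusion.** Wrong as written, and minor. Followed literally, the height row labels as PCS abnormal any subject who averages about 2.1 to 2.3 cm/year or more from screening to Month 24, and it can never flag a subject under 18 who does not grow. An adult whose growth is complete can meet it only through a measurement or recording error. The weight-gain rule shares the lack of age adjustment.

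The threshold velocity rests on the stated 3 to 5 months from screening to infusion, 24 months of follow-up and a roughly constant growth rate. That zero growth is never flagged needs no assumption. The number of subjects affected cannot be computed, because the documents give neither the number of adolescents nor their growth rates, and older adolescents who have stopped growing would not be flagged. No efficacy result is touched.

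**What to change.** Edit SAP Table 10 and the text of Section 4.6.4:

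- Remove the height-gain flag, or keep it only as a data-quality check outside the PCS table.
- For subjects under 18 at baseline, convert the height and weight already collected to age- and sex-standardised z-scores, and summarise the change from baseline by visit.
- Add a low-side criterion for the change in height z-score, chosen and prespecified by the sponsor. The documents offer no basis for a particular cut-off, so none is proposed here.
- Keep the raw 10% weight rule for adults.

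This matches what the SAP does elsewhere: age- and sex-specific laboratory ranges (Section 4.6.3), bone density Z scores (Section 4.4.4) and a separate eGFR formula under age 18 (Section 4.4.3.4 and Appendix 6.5). The cost is a table edit and a growth reference in the programming. It needs no new data and leaves every efficacy analysis unchanged.
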